15.2 Guidance on monitoring of patients with infections

All infections that develop during the study will be reported as AEs on the appropriate eCRF capturing AEs. Treatment and additional evaluations will be performed at discretion of the Investigator.

The Investigator should remind the patient of the risk of infections and instruct them to promptly report any symptoms of infections to the Investigator. The patients must also be reminded to always carry their Patient Information Card (with site contact information and which identifies them as participants in a clinical study with investigational and control agents with potential immunosuppressive effects) and to show this to any local healthcare provider they may consult and ask that the Investigator be contacted.

In the case of suspected or confirmed serious (CTCAE, Grade 3-4) or atypical infection, study drug interruption should be considered. The Investigator should inform the Sponsor Medical Advisor of any such cases.

When evaluating a patient with a suspected infection, the most sensitive tests available should be used (i.e. that directly detect the pathogen, as with PCR).

The Investigator should consider early treatment with specific antimicrobial therapy on the basis of clinical diagnosis or suspicion thereof in consultation with infectious disease experts, as appropriate. The Investigator should inform the Sponsor Medical Advisor of any such cases.

Investigators should consider the added immunosuppressive effects of corticosteroid therapy for treatment of MS attack/relapse and increase vigilance regarding infections during such therapy and in the weeks following administration.

In oncology patients treated with ofatumumab, cases of fatal HBV reactivation and fatal infection due to hepatitis B in patients who have not been previously infected have occurred (refer to local ARZERRA® prescribing information). This study excludes the patients who are at potential risk of HBV reactivation (See [Section 4.2](#) Exclusion criterion 10). In patients with suspicion of HBV infection during the study, laboratory testing for HBV should be done. For patients who show new evidence of HBV infection [HBs antigen positive (regardless of antibody status) or HBs antigen negative but HBc IgM/IgG antibody positive], the Investigator is advised to consult with physicians with expertise in managing hepatitis B regarding monitoring and consideration for HBV antiviral therapy.

Patients with new active HBV infection should immediately discontinue study drug and institute appropriate treatment and follow-up.

15.3 Guidance on immunization

The safety of and ability to generate a primary or anamnestic response to immunization with live, live-attenuated or inactivated vaccines during ofatumumab treatment has not been investigated. The response to vaccination could be impaired due to B-cells depletion.

It is recommended that the Investigator review the patient's immunization history as part of the initial Screening procedure for a patient being considered for treatment with ofatumumab. Vaccination of the patient, in compliance with local area vaccination guidelines for the patient population being treated, is recommended prior to administration of ofatumumab. In particular, prior to administration of ofatumumab, hepatitis B vaccination, in patients with risk factors for hepatitis B infection or in areas with a high prevalence of hepatitis B, as per local area treatment guidelines should be considered.

Administration of live or live-attenuated vaccines must be avoided during and after treatment with ofatumumab and until B-cell counts are normalized.

15.4 Guidance on monitoring of patients with low immunoglobulin levels

After baseline, the immunoglobulin levels (IgM and IgG) will be measured at Week 4, 12, 24, 28, 36, 48, subsequent visit for every 12 weeks, and EOS by the central laboratory and will be blinded to the Sponsor and the Investigator. They will only be communicated to the site after

baseline in case of notably low levels. A notably low IgG level is defined as a level that is 20% below the LLN and a notably low IgM level is defined as a level 10% below the LLN. Following notification, the immunoglobulin level should be repeated within 2 weeks by the central lab to confirm the reading. If the repeated test confirms the immunoglobulin level to be below the threshold, the study drug must be discontinued and the immunoglobulin levels needs to be monitored at the Investigator's discretion until levels return back to normal limits. The patient should be evaluated and monitored for infections on a regular basis. Immunoglobulin substitution therapy as pert local medical practice is allowed. Re-initiation of the study drug can only be considered once the immunoglobulin levels are back within normal limits.

Clinical Development

OMB157/Ofatumumab

COMB157G1301 / NCT03249714

A 24-week, randomized, double-blind, placebo-controlled, parallel-group, multicenter study to evaluate the efficacy, safety and pharmacokinetics of ofatumumab in patients with relapsing multiple sclerosis followed by an extended treatment of at least 24 weeks with open-label ofatumumab

Statistical Analysis Plan (SAP)

Author: Statistician, [REDACTED]
Document type: SAP Documentation
Document status: Final v1.0 for final analysis
Release date: 4-September-2020
Number of pages: 61

Document History – Changes compared to previous final version of SAP

Date	Time point	Reason for update	Outcome for update	Section and title impacted (Current)
09-Mar-2018	Prior to FPFV	Creation of final version	N/A - First version	NA
13-Dec-2019	Prior to DBL	Amendment 1	
The variable “Gd-enhanced T1 lesion” was renamed “Gd-enhanced lesion”.
 
Overall rules on Cut-off 1 and Cut-off 2/EOS analyses are additionally mentioned.
 
Documentation was updated to define “1 month”.
 
It was clarified that visit windows are based on study days relative to Core part Day 1.
 
Extension FAS was defined for efficacy analysis including Extension part.
 
Analysis plan on medical history was documented independently.
 
Analysis plan on smoking/alcohol history was documented independently.
 
Definition of time-at-risk was updated for AE analysis.
 
Analyses plans were added for impact assessment on potential unblinding issue.
 
It was clarified which safety analysis to repeat for Cut-off 2/EOS analysis
	
Overall except “1 Introduction” and “3 Sample size calculation”
 
2.1 Data analysis general information
 
2.1.1 General definition
 
2.1.2 Visit windows for data analysis
 
2.2 Analysis sets
 
2.3.4 Medical history
 
2.3.5 Smoking
 
2.4.1 Study treatment / compliance
 
2.7.3 Impact assessment of potential unblinding
 
2.8.1 Adverse events (AE)
 
2.8.1 Adverse events (AE)
 
2.8.3 Laboratory data
 
2.8.4.2 Vital signs.

Date	Time point	Reason for update	Outcome for update	Section and title impacted (Current)
				2.8.4.3 Suicidality evaluations
			Analyses of AE leading to study drug interruption, AE by onset period, subgroup analyses of AE, and analysis of drug-related CDS risks were added.	2.8.1 Adverse events (AE)
			Documentation on liver and renal events was updated	2.8.3 Laboratory data
			Analysis plan for suicidality evaluation was updated.	2.8.4.3 Suicidality evaluations
			[REDACTED]	[REDACTED]
			Section "Analysis for Japan CTD" was removed, and relevant analysis plans were moved to the section for adverse events Also, box plots of lab parameters were cancelled.	N/A
			The imputation rule was updated for relapse.	5.1 Imputation rules.
			CTCAE grade is displayed in the document	5.3.4 CTCAE grades for laboratory parameters
			PD "INCL01A" was added.	5.6 Rule of exclusion criteria of analysis sets
			"Randomization despite screen failure" was added to non-PD criteria.	5.6 Rule of exclusion criteria of analysis sets
20-Jul-2020	Prior to W48 DBL	Amendment 2 for Cut-off 2 analysis	The visit windows for Cut-off 2 analysis were updated.	2.1.2 Visit windows for data analysis
			Definitions of Extension FAS was updated. Extension safety set was additionally defined	2.2 Analysis sets 2.2 Analysis sets
			Description on summary of PD was added.	2.3.1 Patient disposition

Date	Time point	Reason for update	Outcome for update	Section and title impacted (Current)
			Data handling on the baseline data was updated.	2.3 Patient disposition, demographics and other baseline characteristics
			Summary on pre-post ofatumumab treatment was added.	2.4.2 Prior, concomitant and post therapies
			Summary on MS relapse characteristics was added.	2.7 Analysis of secondary efficacy objective(s)
			The analysis plan for AE by onset period was refined.	2.8.1 Adverse events
			Efficacy analysis for Cut-off 2 were additionally documented.	2.15 Analysis on the Extension part not mentioned in the previous sections
			Abnormality criteria was added on AST.	5.3.2 Newly occurring liver enzyme abnormalities.
4-Sep-2020	Prior to final DBL	For final analysis	Analysis sets for patient disposition and baseline data were updated to FAS	2.3 Patient disposition, demographics and other baseline characteristics
			“Gd-enhanced/enhancing lesions” was updated to “Gd-enhanced/enhancing T1 lesions” to align with study protocol and for consistency within this document.	Overall, wherever applicable

Table of contents

Table of contents	5
List of abbreviations	8
1 Introduction	10
1.1 Study design.....	10

5.3.4	CTCAE grades for laboratory parameters.....	53
5.4	Clinical notable vital signs.....	55
5.5	Statistical models	55
5.5.1	Primary analysis	55
5.5.2	Key secondary analysis	55
5.6	Rule of exclusion criteria of analysis sets.....	56

5.7	Statistical method details for TEAEs.....	59
5.7.1	Odds ratios and 95% confidence interval.....	59
5.7.2	Exposure adjusted incidence rate and 95% confidence interval	60
6	Reference.....	61

List of abbreviations

AE	Adverse event
ADA	Anti-drug-antibody
ALP	Alkaline Phosphate
ALT	Alanine Aminotransferase
ARR	Annualized Relapse Rate
AST	Aspartate Aminotransferase
ATC	Anatomical Therapeutic Classification
BIL	Bilirubin
BMI	Body Mass Index
C-CASA	Columbia Classification Algorithm for Suicide Assessment
█	█
█	█
CSR	Clinical Study report
CTC	Common Toxicity Criteria
CTCAE	Common Terminology Criteria for Adverse Events
(e)CSSRS	(electronic) Columbia Suicide Severity Rating Scale
DMC	Data Monitoring Committee
FAS	Full Analysis Set
eCRF	Electronic Case Report Form
ECG	Electrocardiogram
(e)EDSS	(electronic) Expanded Disability Status Scale
EOS	End of Study
FAS	Full Analysis Set
FDA	Food Drug Association
FU	Follow up
Gd	Gadolinium
GGT	Gamma-Glutamyltransferase
INR	International Normalized Ratio
ITT	Intention to treat
IRR	Injection related reaction
KM	Kaplan-Meier
LLN	Lower limit of Normal
M	Month
MedDRA	Medical Dictionary for Drug Regulatory Affairs
MRI	Magnetic Resonance Image
MS	Multiple Sclerosis
NCI	National Cancer Institute
█	█
o.d.	Once Daily
OS	Overall Survival
PD	Pharmacodynamics
PDS	Programming Datasets Specification

PFS	Progression-Free Survival
PH	Proportional Hazard
PK	Pharmacokinetics
PPS	Per-Protocol Set
PRO	Patient-reported Outcomes
PT	Preferred term
qd	Qua'que di'e / once a day
QoL	Quality of Life
RAP	Report and Analysis Process
SAE	Serious Adverse Event
SAF	Safety Set
SAP	Statistical Analysis Plan
SAS	Statistical Analysis Software
	
SOC	System Organ Class
TBIL	Total Bilirubin
TEAE	Treatment Emergent AE
TFLs	Tables, Figures, Listings
ULN	Upper Limit of Normal
WHO	World Health Organization

1 Introduction

The purpose of Statistical Analysis Plan (SAP) is to describe the implementation of the statistical analysis planned in the protocol of study COMB157G1301. Protocol version 01 has been referenced at the time of finalization of the SAP.

The **Double-blind treatment period** will start on Day 1 with randomization of the patient. Patients will be randomly assigned in a 2:1 ratio to receive either ofatumumab 20 mg sc or matching placebo sc in a double-blind fashion. Injectable study treatments (ofatumumab or

placebo) will be administered on Day 1, Day 7, Day 14, Week 4 and every 4 weeks thereafter. The Double-blind treatment period will continue until the completion of all assessments required for the Core part at Week 24.

Patients who prematurely discontinue double-blind study medication will have their end of Study (EOS) visit as soon as possible and will be followed up for safety in the Safety FU period for a minimum of 36 weeks.

The Extension part consists of 2 periods; **Double-blind loading dose period** and **Open-label treatment period**.

The **Double-blind loading dose period** will be applicable for patients who complete the Double-blind treatment period. All patients will receive ofatumumab 20 mg sc at Week 24; the Extension part starts with the injection of the Week 24. Patients randomized to ofatumumab in the Double-blind treatment period will receive the matching placebo sc at Week 25 and 26. Patients randomized to placebo in the Double-blind treatment period will receive ofatumumab 20 mg sc at Week 25 and 26. All patients will receive the study drug in a double-blind manner at Week 25 and 26.

The **Open-label treatment period** will begin at Week 28 and all patients will receive open-label ofatumumab 20 mg sc every 4 weeks in this period. This period will continue until the last patient is transferred to a planned umbrella extension study (under separate protocol requiring another informed consent).

Patients who prematurely discontinue study treatment will have their EOS visits as soon as possible and will be followed up for safety in the Safety FU period for a minimum of 36 weeks. After study drug discontinuation, during Core or Extension parts, patients may initiate alternative MS therapy according to local standard of care if clinically indicated.

The **Safety FU period** will be applicable for the following patients:

- Patients who complete this study and do not enter the planned umbrella long-term extension study
- Patients who prematurely discontinue study treatment in Core or Extension part

All Safety FU visits must be scheduled relative to the date of EOS visit.

[figure not shown]
These patients will be followed for a total of at least 36 weeks after study drug discontinuation (by 36 weeks the majority of patients are expected to have repleted their circulating B-cells, see Protocol Section 3.3).

A longer than 36 weeks of post-treatment Safety FU period will be required for patients who have not repleted their B-cells (i.e. B-cells not back to baseline value or to lower limit of normal (LLN) whichever comes first as determined by central lab) at 36 weeks.

These patients will continue to be followed with assessments every 12 weeks until their B-cell counts have repleted. To protect the study blind, the assessment of B-cell counts will be performed centrally and the Investigators and Sponsor study team will only be informed of whether or not continued follow-up is necessary.

Patients who have initiated therapy with another disease modifying/immunosuppressive therapy before the end of the 36-week follow-up will not be monitored beyond 36 weeks.

Figure 1-1 Study design

* Patients randomized to placebo in the Double-blind treatment period will receive ofatumumab 20 mg sc at Week 24, 25 and 26 as loading dose regimen. Patients randomized to ofatumumab in the Double-blind treatment period will receive ofatumumab 20 mg sc at Week 24 and the matching placebo sc at Week 25 and 26. In all patients, the extension part starts with the Week 24 injection.

** Patients who prematurely discontinue study drug or patients who do not enter the umbrella extension study will enter the Safety FU period following their EOS visits.

*** Umbrella extension study (planned) will be conducted under separate protocol.

Data cut-off 1 is defined as the date the last patient completes all the assessments for Week 24.

Data cut-off 2 is defined as the date the last patient completes all the assessments for Week 48.

Three types of analyses to be conducted are described in the SAP. They will be referred to in this document as Cut-off 1 analysis, Cut-off 2 analysis, and EOS analysis:

1. The Cut-off 1 analysis will be conducted for the Core part. Data up to the Week 24 (cut-off 1) will be used. Data from the safety FU period for patients who prematurely discontinued from study treatment before Week 24 will also be included. The analysis will be performed when the last patient has completed the double-blind loading dose period at Week 28. This analysis will be used in support of the registration of ofatumumab in Japan.
2. The Cut-off 2 analysis will be conducted when the last patient completes all assessments up to the Week 48 visit. The analysis will also include assessments of maintenance of efficacy and extended safety during the extension part and data from the Safety FU period for patients who prematurely discontinued from study treatment before the cut-off 2. Any between treatment comparison will be based on treatment assignment in the core part. The analysis will also be used in support of the registration of ofatumumab in Japan.
3. The final analysis will be conducted when the last patient completes the EOS visit or Safety FU period.

1.2 Study objectives and endpoints

Primary objective

The primary objective of the study is to demonstrate that ofatumumab is superior to placebo in reducing the cumulative number of Gd-enhanced T1 lesions across 4 MRI scans at Week 12, 16, 20 and 24 in patients with relapsing MS. The primary objective will be assessed during the core part. ([Section 2.5](#))

Secondary objectives

The secondary objectives are described separately for the core part and the extension part:

Core part

Assess the consistency of the efficacy of ofatumumab versus placebo across regions (Japan vs other countries) in the cumulative number of Gd-enhanced T1 lesions on MRI scans at Week 12, 16, 20 and 24. ([Section 2.5.4](#))

Assess the efficacy of ofatumumab versus placebo in the number of new or enlarging T2 lesions on MRI scans. ([Section 2.7](#))

Assess the efficacy of ofatumumab versus placebo in annualized relapse rate (ARR) and time to first relapse. ([Section 2.7](#))

Assess the safety and tolerability of ofatumumab versus placebo. ([Section 2.8](#))

Assess the similarity of the pharmacokinetics (PK) and B-cell count following the treatment with ofatumumab across regions (Japan vs other countries). ([Section 2.9](#), [Section 2.10](#), [Section 2.8](#))

[figure not shown]
Extension part (additional to objectives for Core part)

Assess extended safety and tolerability of ofatumumab. ([Section 2.8](#))

Assess extended efficacy of ofatumumab in:

- Number of Gd-enhanced T1 lesions ([Section 2.5](#))
- Number of new or enlarging T2 lesions ([Section 2.7](#))
- Annualized relapse rate ([Section 2.7](#))
- Time to first relapse ([Section 2.7](#))

Assess the PK and B-cell count following the extended treatment with ofatumumab. ([Section 2.9](#), [Section 2.10](#), [Section 2.8](#))

2 Statistical methods

2.1 Data analysis general information

Data will be analyzed by Novartis statistical and programming team according to the data analysis Section 9 of the study protocol which is available in Appendix 16.1.1 of the CSR. Important information is given in the following sections and details are provided, as applicable, in Appendix 16.1.9 of the CSR.

SAS (version 9.4 or higher) will be used for generating study outputs used for clinical reports.

Unless otherwise stated, summary tables/figures/listings will be on all subjects included in the population under consideration. Data will be summarized with respect to demographic and baseline disease characteristics, efficacy, and safety assessments.

The three analysis conducted at:

- Cut-off 1 (Core part data up to Week 24 visit),
- Cut-off 2 (all data obtained until the last patient completes all assessments up to Week 48 visit),
- Final, when the last patient completes the EOS visit or Safety FU period.

Each analysis will be conducted on all subject data available at the corresponding cut-off. Cut-off 2 and final *safety* analysis will include only each patient's assessments under ofatumumab treatment or during Safety FU.

In these analyses, data from Safety FU period will be analyzed separately if necessary.

The stratification factors, which are the number of Gd-enhanced T1 weighted lesions at baseline (0 or ≥ 1) and region (Japan or non-Japan), will be included in subgroup analysis where appropriate.

2.1.1 General definitions

Study drug/treatment refers to the investigational drug Ofatumumab and placebo.

“Date of Cut-off 2” is expected as the date the last patient completes all assessments at Week 48 visit. If the last patient discontinues from the study prior to Week 48 visit, “date of Cut-off 2” is the last patient's last visit.

Date of first administration of study drug/treatment, or first date of study drug/treatment, is defined depending on the analysis purposes.

- For Cut-off 1 analysis and Cut-off 2 and final *efficacy* analysis, it refers to the date when the first dose of randomized treatment is administered.
- For Cut-off 2 and final *safety* analysis, it refers to the date when the first dose of ofatumumab is administered.

Date of last administration of study drug/treatment, or last date of study drug/treatment is defined by analysis time point.

- For Cut-off 1 analysis, it refers to the date when the last dose of randomized treatment is administered up to Week 24 visit.
- For Cut-off 2 analysis, it refers to the date when the last dose of treatment is administered up to the date of Cut-off 2.
- For final analysis, it refers to the date when the last dose of treatment is administered up to EOS visit.

Study day is defined as: if after first date of study drug, then (Study Day) = (Date) – (first date of study drug) +1; if before first date of study drug, then (Study Day) = (Date) – (first date of study drug); Study Day 1 is defined as the date of the first administration of study drug; there is no Study Day 0.

Duration of an event is calculated as (event end date) – (event start date) +1.

1 month is counted as 30 days unless otherwise specified.

Baseline is defined for each cut-off analysis.

- For Cut-off 1 analysis, and Cut-off 2 and final *efficacy* analysis, baseline is defined as the last non-missing result before or on the first date of study drug.
- For Cut-off 2 and final *safety* analysis, definition of baseline depends on each patient's treatment course in the study
 - For a patient continuously having ofatumumab across Core and Extension parts, baseline is defined as the last non-missing result before or on the first date of study drug.
 - For a patient switching the treatment from placebo to ofatumumab when entering the Extension part, baseline is defined as the dose date of ofatumumab at Week 24. *For analysis on vital signs*, the baseline is defined as *the pre-dose measurement* at Week 24.

On-treatment period is defined as the one between the first date of study drug and 30 days after the last date of study drug. The on-treatment definition applies to efficacy analyses only.

“Safety cut-off” is defined as 100 days after the last dosing date of the study drug.

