5. After Week 36 visit, patients may visit every 12 weeks. In this case, patients will need to continue study treatment every 4 weeks at home. For PK and ADA visits the patient should not take injection before coming to the site (see footnote 12).
6. S/A/A means Steroid/Acetaminophen/Antihistamine. Premedication with acetaminophen and/or antihistamines (or equivalent) is recommended and may be administered at the discretion of the Investigator. For the first injection of Double-blind treatment period (Day 1) and Double-blind loading dose period (Week 24) only, the addition of premedication with steroids (methylprednisolone 100 mg iv or equivalent) is recommended. Premedication should be administered 30 to 60 min prior to study drug injection.
7. Vital signs should be obtained 30-60 min before sc injection (if premedication is administered, pre-injection vital signs should be obtained before premedication is administered), and again approximately 60 min post-injection on Day 1, 7, 14 and Week 4 in the Core part and on the first injection in the Extension part (at Week 24).
8. A complete physical examination will be performed at the visits indicated in [Table 6-1](#) and will include an assessment of skin, head and neck, lymph nodes, heart, lungs, abdomen, back, neurological function and comments on general appearance. A complete neurological examination will be part of the initial physical examination at Screening.
9. a) Assessment can be conducted either at Screening OR Baseline visit. b) Assessment can be conducted at either the Baseline OR the Day 1 visit (they must be conducted before the first dose of investigational treatment).
10. Pregnancy test is conducted on female patients only: Serum pregnancy tests will be conducted at Screening and EOS visit. Urine pregnancy tests will be conducted at all other planned visits as indicated in [Table 6-1](#). After Week 28, 4-weekly urine pregnancy tests will be conducted at home between site visits. The patient must contact the Investigator immediately in the case of a positive test for confirmatory testing at the Investigator's discretion.
11. Patient's contraception status must be reviewed and documented to ensure method of contraception continues to be appropriate per protocol requirement for highly effective contraception.
12. PK and ADA visits: The PK (Plasma) and ADA (Serum) samples should be drawn before the patient takes their injection.

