6.5.2 Vital signs

Vital signs will include sitting pulse rate (measured as radial pulse for 60 seconds), sitting systolic and diastolic blood pressure and body temperature (oral, or per local practice) which will be assessed at the visits indicated in [Table 6-1](#) and [Table 6-2](#).

For the injections on Days 1, 7, 14 and Week 4 in the Core part and on the first injection in the Extension part (at Week 24), vital signs should be obtained 30-60 min before sc injection and again approximately 60 min post-injection. If pre-medication is administered, the vital signs should be taken prior to pre-medication administration.

After the patient has been sitting for five min, with their back supported and both feet placed on the floor, systolic and diastolic blood pressure will be measured 3 times using an automated validated device (manual sphygmomanometer may be used if automated device is not available at the study site). The repeat sitting measurements of blood pressure and pulse will be made at 1-2 min intervals. If an automated blood pressure device is used, it will need to have been calibrated according to the manufacturer's guidelines. In case the cuff sizes available are not large enough for the patient's arm circumference, a manual sphygmomanometer with an appropriately sized cuff may be used.

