Table 2-7 Visit windows for vital signs: Cut-off 1 analysis

Visit-window	Start day	Target day	End day
Week 8	1	56	70
Week 12	71	84	98
Week 16	99	112	126
Week 20	127	140	168

*if study goes beyond Week 72, every 12 weeks the same assessments on Week 60 and Week 72 will be performed. X will be a multiple of 12 weeks from Week 84 and beyond.

Data collected from Day 1, Day 7, Day 14, Week 4, and Week 24 are collected differently and not re-mapped.

Day counts are relative to the first date of study drug in the Core part.

Table 2-8 Visit windows for vital signs: Cut-off 2 and final analysis

Visit-window	Start day	Target day	End day
Week 12	1	84	126
Week 36	211	252	294
Week 48	295	336	378
Week 60	379	420	462
Week 72	463	504	546
Week x*	$x * 7 - 42 + 1$	$x * 7$	$x * 7 + 42$

Visit-window	Start day	Target day	End day
*if study goes beyond Week 72, every 12 weeks the same assessments on Week 60 and Week 72 will be performed. X will be a multiple of 12 weeks from Week 84 and beyond.			
Data collected from Week 24 are not re-mapped, because they are collected at pre- and post-dose and will not be included in by-visit summary.			
Day counts are relative to the first date of ofatumumab.			

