2.8.4.2 Vital signs

Vital sign measurements and their change from baseline will be summarized with descriptive (mean, median, standard deviation, min, max) by visit window. The number and percentage of subjects with clinically notable vital signs will be presented.

Vital sign measurements include sitting systolic and diastolic blood pressure, sitting pulse, body temperature, height and body weight.

Three sitting measurements of blood pressure (SBP and DBP) and pulse will be taken at each vital sign assessment.

For post baseline assessments, the blood pressure and pulse values will be the average of the non-missing values of the 3 measurements. If more than one blood pressure/pulse assessment (scheduled or unscheduled) exists in a particular visit-window ([Section 2.1.2](#)) the blood pressure/pulse value will be the average of all assessments. Derivation of baselines for blood pressure and pulse are provided in [Section 2.1.1](#).

Height will be collected at screening visit only and will be summarized in the baseline characteristic summary only.

Analyses of vital sign measurements (excluding data collected on Day 1, Day 7, Day 14, Week 4 and Week 24) using descriptive summary statistics (mean, median, standard deviation, min, max) for the change from baseline for each post-baseline visit-window will be performed. These descriptive summaries will be presented by vital sign parameter and treatment group. Change from baseline will only be summarized for patients with both baseline and post-baseline values.

The number and percentage of patients with clinically notable vital signs will be presented. For clinical notable vital signs values, refer to [Section 5.4](#). This analysis will be repeated for Cut-off 2 analysis.

For vital signs data collected on Day 1, Day 7, Day 14, Week 4, and Week 24 protocol scheduled visit, pre and post-injection vital signs data including temperature, pulse rate and blood pressure are collected. Change from pre-injection to post-injection in these 3 parameters will be summarized by nominal visit. This analysis will be performed for Cut-off 1 analysis only.

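### The date-only baseline rule in SAP 2.1.1, read literally, takes the Day 1 post-injection blood pressure, pulse and temperature as baseline

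*SAP*

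**What the plan says.** SAP 2.1.1 gives the general rule: "baseline is defined as the last non-missing result before or on the first date of study drug". It governs Cut-off 1 for both arms. At Cut-off 2 and final safety analysis it governs patients who receive ofatumumab through both parts. The reference point is a date, since "Study Day 1 is defined as the date of the first administration of study drug".

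For placebo patients who start ofatumumab at Week 24, the same section adds a condition for vital signs: their baseline is "the pre-dose measurement" at that visit. Day 1 has no matching condition.

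Protocol 6.5.2 states that on the listed injection days, Day 1 among them, "vital signs should be obtained 30-60 min before sc injection and again approximately 60 min post-injection". Table 6-1, footnote 7, repeats it: "and again approximately 60 min post-injection on Day 1, 7, 14 and Week 4 in the Core part". Both places put the pre-injection set ahead of any premedication.

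SAP 2.8.4.2 has no vital-sign baseline rule of its own. It says "Derivation of baselines for blood pressure and pulse are provided in" Section 2.1.1. SAP 2.1.2 likewise refers all baseline definitions to 2.1.1.

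**The concern.** A baseline should describe the patient before treatment. Here the last record dated on Day 1 follows both premedication and the first injection. Protocol 5.5.7 recommends adding a steroid to the Day 1 premedication, so that reading can reflect steroid, acetaminophen, antihistamine and study drug together. Among the symptoms of injection systemic reactions, SAP 2.8.1.1.1 lists hypotension, hypertension, tachycardia and fever. These concern the very parameters for which the baseline would be taken.

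Any acute movement in that first period would be carried, with its sign reversed, into every later change from baseline. At Cut-off 2 and final, the two displayed groups could also have baselines on opposite sides of an injection: before it for switchers and after it for continuous patients.

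**Working it through.** The plan states no figure that depends on this rule. The check applies the rule to the schedule and then traces which outputs use the result.

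**1. Candidate records.** Protocol Table 6-1 schedules vital signs at Screening, at the Baseline visit and on Day 1; the next set is on Day 7. Day 1 has a set 30 to 60 min before injection and another about 60 min after. Premedication is given 30 to 60 min before injection, so the second set falls about 60 + 30 = 90 to 60 + 60 = 120 min after premedication.

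**2. Record selected under each reading.**

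| Reading | Baseline record |
|---|---|
| SAP 2.1.1 as written | Day 1, about 60 min after injection |
| As written, post-injection set missing | Day 1, before injection |
| Last record before the first injection | Day 1, before injection |
| All Day 1 data barred, for baseline too | Baseline visit |

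Under the rule as written, patients with and without a post-injection set would also have baselines of different kinds.

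**3. Effect on change from baseline.** Let Y_v be the value at a later visit, Y_pre and Y_post the two Day 1 values, and d = Y_post − Y_pre. Then

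Y_v − Y_post = (Y_v − Y_pre) − d.

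Each change is displaced by −d. With mean shifts d_o on ofatumumab and d_p on placebo, the difference between arms is displaced by −(d_o − d_p).

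The documents give neither d_o nor d_p. The values below are assumptions that show only how the formula behaves, in the units of the parameter:

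| Assumed d_o | Displacement if d_p = 0 | Displacement if d_p = 2 |
|---|---|---|
| 0 | 0 | +2 |
| 2 | −2 | 0 |
| 5 | −5 | −3 |
| 10 | −10 | −8 |

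An equal shift in both arms cancels in the comparison but still distorts each arm's own summary.

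**4. Outputs that use the rule.**

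- *Affected:* the change-from-baseline summary of blood pressure, pulse and temperature at Cut-off 1. SAP Table 2-7 gives it windows at Weeks 8, 12, 16 and 20.
- *Affected if produced:* the same summary at Cut-off 2 or final for continuous-ofatumumab patients. Table 2-8 sets windows for it, but 2.8.4.2 expressly repeats only the notable-value analysis at Cut-off 2.
- *Not affected:* weight, which Table 6-1 does not schedule on Day 1, and so the 7% weight criterion; the notable limits for pulse, blood pressure and temperature in SAP 5.4, which are absolute; the pre-to-post injection summary, which uses the pre-injection value directly; and all efficacy analyses.

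**The case against.** The best defence is in SAP 2.8.4.2, which describes the change-from-baseline work as "Analyses of vital sign measurements (excluding data collected on Day 1, Day 7, Day 14, Week 4 and Week 24"). A note to Table 2-7 adds: "Data collected from Day 1, Day 7, Day 14, Week 4, and Week 24 are collected differently and not re-mapped". If Day 1 data are out of the analysis, the post-injection set cannot be the baseline, and the Baseline-visit value would serve.

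This has some force but does not repair the rule. In context the exclusion settles which records enter the post-baseline windows, as the table note does. The same section still sends the reader to 2.1.1 for baseline. Even if the exclusion did reach baseline, it would give a third answer and not the Day 1 pre-dose value. At most it makes the text ambiguous.

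It is also fair to say that a pre-dose baseline was probably intended, given the Week 24 wording, and that programming specifications outside these documents may already apply it. The SAP does not say so for Day 1.

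Two stronger readings are tempting.

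- *A known imbalance between arms.* Protocol 1.1 reports injection-related reactions in 52% on ofatumumab and 15% on placebo, mainly after the first dose. A reader might infer that the baseline is distorted more on ofatumumab. Those figures come from an earlier study, pool regimens of 3, 30 and 60 mg where this trial uses 20 mg, and count adverse events, 97% of them mild or moderate. They are not vital signs measured at one hour. The premedication advice is also the same in both arms. The figures make an imbalance possible but do not establish one.
- *Damage to every vital-sign output.* A reader might extend the point to weight, notable values or shift tables. The first two are unaffected for the reasons in the working, and the SAP plans no vital-sign shift tables; its shift tables are for laboratory data.

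**Conclusion.** The point holds within a narrow scope. Read literally, SAP 2.1.1 gives a baseline for blood pressure, pulse and temperature that follows premedication and study drug, and no other text corrects it. This goes beyond missing detail, because the stated rule returns the wrong record whenever the post-injection set exists.

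The reach is one descriptive safety summary at Cut-off 1, covering both arms of the 60 planned patients. It may extend to its counterpart at Cut-off 2 or final for continuous-ofatumumab patients. No hypothesis test, endpoint or decision rule depends on it. The acute effect of injection is still properly described by the separate pre-to-post summary.

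The conclusion assumes that the post-injection set is recorded as scheduled and that the rule is programmed as written. The size and direction of the bias, and whether it differs between arms, cannot be computed from the documents.

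**What to change.** Add one sentence to SAP 2.1.1, limited to vital signs: baseline is the last non-missing assessment before the first injection, meaning the Day 1 set taken before injection and premedication, or the most recent earlier value if that set is missing. This matches the rule already written for Week 24 switchers and gives both groups at Cut-off 2 and final the same kind of baseline.

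Keep the change to vital signs. Redefining baseline by date and time for every variable would go beyond the defect. EDSS, for example, may properly be done on Day 1 before dosing, and the documents do not say that its clock time is recorded.

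While editing, state how the three replicate readings of blood pressure and pulse are combined at baseline; 2.8.4.2 gives the averaging rule only for post-baseline assessments.

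No new data are needed, because pre- and post-injection sets are already collected separately. The current SAP was issued before the final database lock, after versions tied to the two earlier locks. For outputs already run, the remaining work is to confirm which Day 1 record was used and to rerun the change-from-baseline tables if it was the post-injection one.
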